## **19. ADMINISTRATIVE PROCEDURES**

### **19.1 Investigator Responsibilities**

The PI will conduct this study in accordance with the current International Conference on Harmonization (ICH) guidance, the Good Clinical Practice (GCP) guidance, the Declaration of Helsinki, FDA regulations, local IRB and legal requirements.

### **19.2 Data and Safety Monitoring Board Protocol Review**

Initial DSMB protocol review will be conducted prior to SRC and IRB submissions.

Any protocol revision or amendment that includes a potential change to any section of data and safety monitoring plan must be reviewed and approved by the DSMB **prior to the protocol amendment submission to the IRB**.

### **19.3 Multicenter Trials**

Not applicable. This is a single center trial.

## **20. SUBJECT CONFIDENTIALITY**

The principal investigator will ensure that the subject's confidentiality is maintained in compliance with Federal regulations, the International Conference on Harmonization (ICH), and Good Clinical Practice (GCP) Guidelines.

Oversight entities and/or regulatory authorities will be permitted direct access to review the subject's original medical records, electronic medical records or certified copies for verification of study-related procedures and data. Direct access includes examining, analyzing, verifying, and reproducing any records and reports that are important to the evaluation of the study.

## **21. STUDY DOCUMENTATION AND ARCHIVE**

The investigator will maintain a list of appropriately qualified persons to whom he/she has delegated study duties. All persons authorized to make entries and/or corrections on CRFs will be included on the Delegation of Responsibilities Form.

Source documents, data, and records from which the subject's CRF data are obtained include, but are not limited to, hospital records, clinical/office/research charts, laboratory and pharmacy records, diaries, microfiches, radiographs, and correspondence. Source data will include information necessary for the reconstruction and evaluation of the trial.

The principal investigator or sponsor-investigator is responsible for maintaining a comprehensive and centralized filing system of all study-related (essential) documentation as required per ICH Guidelines. This can be accomplished by the PI, through the site's standard operating procedures and/or the institutions infrastructure.

The investigator will follow ICH Good Clinical Practice Guidelines and the Code of Federal Regulations for records and record retention.

## **22. DATA**

Applicable data as specified as required in the protocol will be reported/submitted in the case report form (CRF). Data reported in the case report forms that are derived from source documents must be consistent with the source documents or the discrepancies must be explained. In addition, data will be entered into

RedCap which is currently being used by many BUMC-T departments for their study data bases.

Additional procedures and assessments may be performed as the institution's standard of care; however, these data should remain in the medical records and should not be provided as part of the clinical study data unless it pertains to a serious adverse event.

The investigator is required to prepare and maintain adequate and accurate case histories that record all observations and other data pertinent to the investigation on each individual administered the investigational product/intervention/device, or employed as a control in the investigation.

At the end of the study, the original samples will be destroyed. Remaining extracted DNA samples will be preserved for further sequencing. All remaining biospecimens will be destroyed after 6 years.

## **23. PROTOCOL DEVIATIONS**

The investigator will conduct the study in conformance with this protocol, generally accepted standards of Good Clinical Practice and all applicable federal, state and local laws, rules, and regulations.

Approvals or waivers for protocol deviations will be obtained from the IRB ***prior to*** occurring, except changes to eliminate an immediate hazard to study subjects. If immediate verbal approval is obtained, it will be documented by the research staff obtaining the approval and followed by a written protocol deviation form per the site standard operating procedures. The sponsor or the sponsor-investigator will sign the Protocol Deviation (Waiver) Approval Form or other similar document. The original will be filed in the regulatory binder and a copy will be placed in the subject's research file.

## 24. KARNOFSKY PERFORMANCE STATUS SCALE DEFINITIONS

Able to carry on normal activity and to work; no special care needed.	100	Normal no complaints; no evidence of disease.
	90	Able to carry on normal activity; minor signs or symptoms of disease.
	80	Normal activity with effort; some signs or symptoms of disease.
Unable to work; able to live at home and care for most personal needs; varying amount of assistance needed.	70	Cares for self; unable to carry on normal activity or to do active work.
	60	Requires occasional assistance, but is able to care for most of his personal needs.
	50	Requires considerable assistance and frequent medical care.
Unable to care for self; requires equivalent of institutional or hospital care; disease may be progressing rapidly.	40	Disabled; requires special care and assistance.
	30	Severely disabled; hospital admission is indicated although death not imminent.
	20	Very sick; hospital admission necessary; active supportive treatment necessary.
	10	Moribund; fatal processes progressing rapidly.
	0	Dead

## 25. COMMON TOXICITY CRITERIA (CTCAE)

CTCAE version 5.0

### Expedited Reporting Requirements for Adverse Events

FDA REPORTING REQUIREMENTS FOR SERIOUS ADVERSE EVENTS (21 CFR Part 312)

NOTE: Investigators MUST immediately report to the sponsor ANY Serious Adverse Events, whether or not they are considered related to the investigational agents(s) intervention (21 CFR 312.64)

An adverse event is considered serious if it results in ANY of that following outcomes:

1. Death
2. A life-threatening adverse event
3. An adverse event that results in inpatient hospitalization or prolongation of existing hospitalization for  $\geq$  24 hours
4. A persistent or significant incapacity or substantial disruptive of the ability to conduct normal life functions
5. A congenital anomaly birth defect
6. Important Medical Events (IME) that may not result in death, be life threatening, or require hospitalization may be considered serious when, based upon medical judgement, they may jeopardize the patient or subject and may require medical or surgical intervention to prevent one of the outcomes listed in the definition (FDA 21 CFR 312.32, ICH E2A and ICH E6).

Toxicity will be scored using CTCAE Version 5.0 for toxicity and adverse event reporting. A copy of the CTCAE Version 5.0 can be downloaded from the CTEP homepage (<http://ctep.cancer.gov>). All appropriate treatment areas should have access to a copy of the CTCAE Version 5.0. The investigator must evaluate each adverse experience for its relationship to the test drug/treatment and for its seriousness.

## 26. STUDY SCHEDULE

Test or Procedure	Baseline (Prior to first treatment)	Week 1 (±1 day)	Week 2 (±1 day)	Week 3 (±1 day)	Week 4 (±1 day)	Week 5 (±1 day)	Week 6 (±1 day)	Week 7 (if applicable) (±1 day)	1-month post-RT follow-up visit (+21 days)	
Informed consent	X									
Medical history, BMI and tobacco history 1	X									
Concurrent meds 2	X		X		X		X		X	
Physical Exam including dental eval and photos 3	X	X	X	X	X	X	X	X	X	
Hct 4	X								X	
Malignancy info 5	X									
Registration & Randomization	X									
OMWQ and PRO CTCAE 6	X		X		X		X		X	
WUS and Microbiome Collection 7	X		X		X		X		X	
Dispense IP/placebo	X	X	X	X	X	X	X	X		
Adverse Event Check 8		X	X	X	X	X	X	X	X	
Rinse Diary and Observational Form 9	X	X	X	X	X	X	X	X	X	

Test or Procedure	Baseline (Prior to first treatment)	Week 1 (±1 day)	Week 2 (±1 day)	Week 3 (±1 day)	Week 4 (±1 day)	Week 5 (±1 day)	Week 6 (±1 day)	Week 7 (if applicable) (±1 day)	1-month post-RT follow-up visit (+21 days)	
Collect Unused IP/placebo 10		X	X	X	X	X	X	X	X	
Documentation of RT treatment interruptions									X	

1= Complete medical history will include demographics and will be performed within 90 days of registration. Tobacco history will be collected using the Tobacco Assessment Questionnaire.

2= Review medications including usage of any chlorine dioxide, antimicrobials, or corticosteroids within last 7 days prior to registration. Additionally, will review usage of honey, baking soda and salt rinses, magic mouthwash, viscous lidocaine, doxepin solution, chlorhexidine, and other antimicrobials, corticosteroids, anti-inflammatories, etc during study period. Only medications related to either cancer therapy or treatment of a related adverse events will be collected. No other concomitant medications will be tracked.

3= All PEs to include vitals (BP, pulse, temperature, weight), KPS scoring, and OM grading per WHO scoring criteria (see section 7.1)

4= Hematocrit within 90 days of study registration

5= Confirmation of cytologic or histologic evidence of HNC and documentation of stage

6= Oral Mucositis Weekly Questionnaire and Patient Reported Outcomes Common Terminology Criteria for Adverse Events

7= Whole Unstimulated Salivary and Microbiome Collection (see section 7.1)

8= Common Terminology Criteria for Adverse Events (CTCAE) v.5 will be used for grading of generalized weakness, skin reaction, weight loss, dry mouth, sore throat, dysphagia, anorexia, dysgeusia, voice alteration, and neck edema

9= Instruct patients on rinse diary to include time, date, and duration of rinses and to note any potential effects thought related to rinse on observation form. Will dispense rinse diary and observation form at baseline visit (prior to the start of week 1 of RT). Will collect and replace both the rinse diary and observation form each week during OTVs

10= Collect and record by volume amount of unused IP/product

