## **4.3 Preclinical Experience**

The safety of chlorine dioxide and its metabolites (chlorite and chlorate) have been studied in animals extensively. Initial evaluations of high dose chlorine dioxide based products have shown adverse hematological, thyroid, and reproductive effects. In a review by Lyman Condie, these animal studies are highlighted in monkey, rat, and mouse experiments, which have shown that at high doses of exposure (>10mg/L or >10mg/kg/d) changes in several key physiologic endpoints have been clearly documented (15). Some studies have shown that chlorine dioxide and its metabolites (chlorite and chlorate) can cause oxidation of hemoglobin into methemoglobin and a subsequent reduction in red cell count by virtue of hemolytic anemia. Other studies have shown decreases in rat T4 levels leading to functional hypothyroidism. Further studies have shown sperm head abnormalities in mice exposed to high levels of chlorine dioxide for 5 days. To our knowledge, no animal studies have specifically evaluated chlorine dioxide in its potential protective effects on OM.

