#### **6.1 Inclusion Criteria**

- a. Able to provide properly obtained written informed consent
- b. Age 18 years or older
- c. Pathologically-confirmed diagnosis of head and neck malignancy (stage I-IV)
- d. Planned to receive high dose RT  $\geq 50$  Gy to visualizable oral cavity and/or oropharyngeal mucosa, with or without administration of concurrent systemic therapy.
- e. Karnofsky Performance Status of  $\geq 60$ , within 90 days of registration
- f. Baseline hematocrit  $> 20$  within 90 days of registration to the study
- g. Willingness to complete OMWQ and PRO-CTCAE forms at each designated time point along with oral rinse diary
- h. Life expectancy  $\geq 3$  months
- i. Willing to tolerate oral rinsing for 30 second intervals
- j. Negative serum pregnancy test in females of childbearing age
- k. Must be willing to use an effective form of birth control if female and of childbearing potential

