#### **9.4 End of IP treatment/Intervention/Device**

Subjects will complete IP the evening prior to their 1-month post-RT follow-up appointment with their Radiation Oncologist.

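### Haematocrit is the only scheduled measure of the haematological risk named in Section 4.3; none is taken during rinsing, and Section 22 keeps routine blood counts out of the study data unless they pertain to a serious adverse event

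*Combined protocol and SAP*

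**What the plan says.** - **The risk.** Section 4.3 reports that "Initial evaluations of high dose chlorine dioxide based products have shown adverse hematological, thyroid, and reproductive effects", and that chlorine dioxide and its metabolites "can cause oxidation of hemoglobin into methemoglobin and a subsequent reduction in red cell count by virtue of hemolytic anemia". Section 6.2 excludes documented G6PD deficiency.
- **The measurement.** The Section 26 schedule marks haematocrit at baseline and at the 1-month post-RT visit, and leaves weeks 1 to 7 blank. Its footnote says "4= Hematocrit within 90 days of study registration". Section 6.1 applies the same limit to the eligibility value, "within 90 days of registration to the study".
- **The exposure.** The rinse starts on the morning of RT day 1. Under Section 9.4, "Subjects will complete IP the evening prior to their 1-month post-RT follow-up appointment with their Radiation Oncologist".
- **Early stoppers.** Under Sections 8.4 and 9.6, patients who come off the rinse stay in assessment up to the 1-month visit unless they withdraw from the study.
- **Adverse events.** Sections 7.1, 11.5 and 26 (footnote 8) name the same ten CTCAE items, none of them haematological. Section 11.5 treats these as a focus and also covers events that may be related to the rinse, radiation or chemotherapy.
- **Routine results.** On additional standard-of-care assessments, Section 22 reads "these data should remain in the medical records and should not be provided as part of the clinical study data unless it pertains to a" (the sentence closes by naming an SAE as the sole exception).
- **Analysis.** Section 17.1 describes no haematocrit analysis.

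**The concern.** The protocol chose haematocrit to follow a risk that it names itself, then scheduled it only before and after exposure. Blood counts drawn in ordinary care during RT or systemic therapy could fill the gap, but Section 22 leaves them in the medical record unless they pertain to a serious adverse event. Nothing in the weekly adverse-event check prompts anyone to look for anaemia.

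The baseline is also loosely tied to the start of rinsing. Section 1.4 admits post-operative patients, so a value up to 90 days before registration may predate surgery.

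At stake is how much the trial can say about haematological tolerability. Section 4.4 states that no safety data are known for this product in this use, and Section 4.2 hopes the results will support a phase III trial. The primary efficacy comparison is not affected.

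**Working it through.** The plan gives no figure for haematocrit, so there is none to reproduce. The check is date arithmetic on the protocol's own windows.

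**Inputs**
- RT length: 6 or 7 weeks (Section 7.1), i.e. 42 or 49 days.
- Follow-up visit: 30 days after RT (Section 2.4), with a window of +21 days (Sections 9.5 and 26), so 30 to 51 days.
- Last rinse: the evening before that visit (Section 9.4).
- Baseline haematocrit: up to 90 days before registration (Sections 6.1 and 26).
- Registration-to-RT interval: not stated. Assumed to be 0 to 14 days.

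**1. Rinse exposure without a scheduled haematocrit** (RT days + follow-up days − 1)
- Shortest: 42 + 30 − 1 = 71 days.
- Longest: 49 + 51 − 1 = 99 days.
- Scheduled haematocrits within it: 0.

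Section 6.2 excludes only planned RT of less than 5 weeks. A 5-week course would give 35 + 30 − 1 = 64 days at the short end.

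**2. Interval between the two scheduled values** (baseline age + registration-to-RT interval + RT days + follow-up days)
- Baseline on RT day 1: 72 to 100 days.
- Baseline 90 days old, RT starting on the day of registration: 90 + 72 = 162 to 90 + 100 = 190 days.
- The same with an assumed 14-day interval: 176 to 204 days.

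The 90 days run to registration, not to the first rinse, so the baseline can be older than 90 days when rinsing starts. The 162 to 204 day figures are upper cases; the documents do not give the typical age of a baseline value.

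**3. Gap from last rinse to the only post-baseline value** (RT days + follow-up days − stop day)
- Completers: less than 1 day.
- Stop on day 14: 72 − 14 = 58 to 100 − 14 = 86 days.
- Stop on day 42: 72 − 42 = 30 to 100 − 42 = 58 days.

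**4. What each group can show**
- Completers: the follow-up value is in effect an end-of-exposure value. Its change from baseline can be compared with placebo. Timing, lowest value, and a fall that recovered before the visit cannot be seen.
- Early stoppers: a fall during exposure could have recovered before the only post-baseline value. If bothersome effects led them to stop, these are patients whose on-rinse values would be of interest.

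**The case against.** The case against making much of this is substantial.

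- **A reader might infer that the trial cannot show whether haematocrit fell on the rinse.** The documents do not support that. Completers are measured about a day after the last rinse, with a concurrent placebo arm, so a net fall can be estimated.
- **A reader might infer that surgery or systemic therapy confounds the comparison.** Both arms are affected alike. The trial is randomised and double-blind, and Section 7.1 stratifies by systemic therapy. An old baseline adds noise and, with about 12 patients per arm, room for chance imbalance, but no systematic bias between arms.
- **A reader might infer that haemolytic anaemia is the one laboratory risk named, or that harm is likely.** Section 4.3 also names thyroid and reproductive effects, all from high-dose exposure. Section 9.3 has the rinse spat out, and Section 4.4 reports human tolerability at low ingested doses.
- **A reader might infer that anaemia is shut out of the data.** Section 11.5 allows a recognised case to be recorded, and Section 22 does not forbid reporting an adverse event.
- **Routine counts may be few.** No section says that counts are drawn during RT, or how often. Those drawn may be clinically triggered, and the lowest of several values tends to fall as more are taken.
- **The study is a pilot**, rated low risk (Section 11.1), and safety is not a listed endpoint.

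These points limit the claim and the remedy. In particular, they rule out a between-arm comparison of lowest values: stratification balances patients at entry, not the number of tests after randomisation. What stands is that no haematocrit is scheduled during exposure, the baseline window is loose, nothing prompts a search for anaemia, and existing results that could help are left out of the dataset.

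**Conclusion.** The concern holds in a limited form. The only scheduled measure of the haematological risk is two haematocrits per patient, with none in about 71 to 99 days of rinsing. A net end-of-exposure change against placebo can be estimated in completers; the course during exposure cannot. In early stoppers the single post-baseline value may reflect weeks off the rinse, about 58 to 86 days for a stop on day 14.

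These figures assume 6 to 7 weeks of RT without interruption and a follow-up visit at 30 to 51 days. RT interruptions would lengthen exposure, because Section 8.3 has the rinse continue through them. The longest baseline-to-follow-up intervals also assume a baseline value at the 90-day limit.

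This is a gap in the safety data that can be narrowed cheaply. It is not evidence that the rinse causes anaemia, and it does not affect the primary analysis.

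**What to change.** Reconcile Sections 4.3, 22 and 26 as follows.

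- **(a) Capture.** Add an exception to Section 22 and a line to Section 26 so that any haematocrit or haemoglobin already drawn as standard care from RT day 1 to the 1-month visit is transcribed with its date.
- **(b) Baseline.** Use the most recent available value before RT day 1 as the safety baseline. The eligibility window can stay as it is.
- **(c) Adverse events.** Add anaemia to the solicited CTCAE items in Sections 7.1, 11.5 and 26 together.
- **(d) Analysis.** In Section 17.1, summarise haematocrit change at the scheduled follow-up visit by arm and systemic-therapy stratum. Describe on-treatment values in fixed time windows, alongside the number of tests per arm. Do not test the lowest value between arms.

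The cost is transcription of existing results, a small addition to the CRF, and an amendment. Because item (c) changes Section 11.5, part of the data and safety monitoring plan, Section 19.2 requires DSMB approval before IRB submission.

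The downside is coverage. The documents do not state how many routine counts exist. They may be sparse, clinically triggered, and different by stratum and by arm, so the on-treatment values are descriptive only. No new blood draw and no clinical rule is proposed.

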## 27. Tobacco Assessment Questionnaire

TOBACCO ASSESSMENT - BASELINE			
REGISTERING INSTITUTION	PARTICIPANT ID	VISIT TYPE	VISIT DATE (MM/DD/YYYY)

Instructions: When a number is requested in the response, please enter a whole number (i.e. "4") and not a range or fraction of a number.
 
Section A. Basic Cigarette Use Information
 
1. Have you smoked at least 100 cigarettes (5 packs = 100 cigarettes) in your entire life?   Yes   No → Skip to Section B   Don't know/Not sure → Skip to Section B
 
2. How old were you when you first smoked a cigarette (even one or two puffs)?  ____ Years old
 
3. How old were you when you first began smoking cigarettes regularly?  ____ Years old   Check here if you have never smoked cigarettes regularly.
 
4. How many total years have you smoked (or did you smoke) cigarettes? Do not count any time you may have stayed off cigarettes.  ____ Years (If you smoked less than one year, write "1.")
 
5. On average when you have smoked, about how many cigarettes do you (or did you) smoke a day? (A pack usually has 20 cigarettes in it).  ____ Number of cigarettes per day
 
6. Do you NOW smoke cigarettes?   Everyday   Some days   Not at all → Skip to question 8
 
7. How soon after you wake up do you smoke your first cigarette?   Within 30 minutes   After 30 minutes
 
8. How long has it been since you last smoked a cigarette (even one or two puffs)?  First check which one of the following choices applies to you. Then, if applicable, write a number on the line for how many days, weeks, months, or years it has been since your last cigarette.
 
 I smoked a cigarette today (at least one puff)   I-7 days → Number of days since last cigarette   Less than 1 month → Number of weeks since last cigarette _____   Less than 1 year → Number of months since last cigarette _____   More than 1 year → Number of years since last cigarette _____   Don't know/Don't remember
 
Section B. Use of Other Forms of Tobacco
 
9. Have you ever used other forms of tobacco, not including cigarettes?   Yes   No → Skip to Section C
 
10. How often do you/did you use other forms of tobacco?   Every day → Number of times per day _____   Some days → Number of days _____ per  Week  Month  Year
 
11. Which of the following products have you ever used regularly?  Check all that apply
 
 Cigarettes   E-cigarettes or other electronic nicotine delivery system   Traditional cigars, cigarillos or filtered cigars   Pipes   Waterpipe   Hookah   Clove cigarettes or kreteks   Bidis   Smokeless tobacco, like dip, chew, or snuff   Snus   Paan with tobacco, gutka, zarda, khani   Other, Please specify: _____
 
12. If you do not currently use other forms of tobacco, but did in the past, how long has it been since you last used other forms of tobacco regularly?   Within the past month (0 to 1 month ago)   Between 1 and 3 months (1 to 3 months ago)   Between 3 and 6 months (3 to 6 months ago)   Between 6 and 12 months (6 to 12 months ago)   Between 1 and 5 years (1 to 5 years ago)   Between 5 and 15 years (5 to 15 years ago)   More than 15 years ago   Don't know/Not sure   Never used other forms of tobacco regularly
 
Section C. Second Hand Smoke Exposure
 
13. Are you currently living with a smoker?   Yes   No
 
14. In the past 30 days, have you lived in a place where other people smoked cigarettes indoors?   Yes   No
 
15. In the past 30 days, have you worked in a place where other people smoked cigarettes indoors?   Yes   No
 
16. Thinking of all your childhood and adult years, have you ever lived in a place where other people smoked cigarettes indoors?   Yes In total, for about how many years? _____ If less than 1, write "1."   No
 
17. Thinking of all the years you have worked, have you ever worked in a place where other people smoked cigarettes indoors?   Yes → In total, for about how many years? _____ If less than 1, write "1."   No
 
Investigator Signature _____ Date ____ / ____ / ____ (MM/DD/YYYY)  Investigator Name (please print) _____
			
